#### **Observation period of efficacy endpoints**

The 24-week on-treatment period for efficacy endpoints (primary and secondary efficacy endpoints) is defined as the time from the first injection of open-label IMP up to 7 days after date of last IMP administration for HbA1c, 0 day for 4-point and 8-point SMPG and insulin dose, 1 day for FPG and fasting SMPG, 2 days for hypoglycemia after the last injection of open-label IMP or up to the introduction of rescue therapy, whichever is the earliest.

The randomized 24–week period for efficacy variables is defined from first dose of IMP up to Week 24, regardless of study treatment discontinuation and intake of rescue therapy.

The baseline value for efficacy endpoints is the last available value prior to the first injection of open-label IMP.

# 9.2.1.1 Fasting plasma glucose

Fasting plasma glucose is measured at a central laboratory.

Blood samples for FPG measurement are taken at baseline (Visit 2; Day 1); at Visit 10 (Week 8); Visit 14 (Week 12); and Visit 20 (Week 24; final primary endpoint assessment visit).

# 9.2.1.2 Self-measured plasma glucose (SMPG) and glucometer, patient diaries and training

# 9.2.1.2.1 Glucometer, patient diary and training

All the patients are supplied with a glucometer, the corresponding supplies (lancets, test strips, etc), a leaflet, and with diaries at the screening visit V1 (Week -2) in order to perform self-

Property of the Sanofi Group - strictly confidential

measurement of plasma glucose, reporting information related to hypoglycemic event and record IMP doses etc. The patients will be instructed in the proper use of the glucometer and diary including education about hypoglycemia symptoms and management (See Section 10.1.1.1) at Visit 1 and repeated at Visit 2 to make sure good compliance to the instruction. The training will be repeated as often as necessary at the study visits. The patients will be instructed to bring their glucometers and patient diaries with them to each site visit.

The glucometers should be calibrated according to instructions given in the package leaflet and the study site should also check the glucometers regularly using the provided control solutions for data validity.

Instruction on how to complete the patient diary on a daily basis will be done by site staff. At each on site visit:

- The study site staff reviews the patient's diary,
- SMPG values stored in the glucometer memory will be downloaded, printed out, dated, signed and filed into the patient file. If the patient has more than one SMPG reading at the same time point, the Investigator/site staff should discuss with the patient to identify the appropriate value to be recorded in the patient diary and in the e-CRF. This information will help the Investigator to assess treatment effects, adjust insulin doses and compliance.

**Note:** The SMPG values to be entered in the e-CRF must be checked for consistency with the information from the glucometer. In case of inconsistency, the reason for inconsistency has to be documented. If needed, the resulting action (eg, training of the patient on correct documentation of the values) is also to be documented. The confirmed values will be entered in the e-CRF based on the glucometer output values.

The **patient diary** includes but is not limited to the following information:

- Time and dose of daily IMP injections and type and dose of daily non-insulin antidiabetic medication(s),
  - In case of missed IMP injection, "0 unit" should be reported during the period when the IMP was not taken,
- Times of start of meals (breakfast, lunch and dinner) and SMPG measurements, as well as plasma glucose values at the day of the 4-point and 8-point SMPG test (see Section 1.2).
- Changes in anti-diabetic medication treatment,
- Adverse events, signs and symptoms suggesting occurrence of hypoglycemia and relevant onset time, countermeasure or corrective treatment, supportive test (ie, SMPG value) and outcome etc.

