# 8.4 BLINDING PROCEDURES

As Toujeo and the control drug Tresiba are distinguishable, this study is an open-label design, and no attempt will be made to blind administration.

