#### COMPENSATION FOR LACK OF BLINDING

Despite the open-label administration of IMP, assessment of outcomes will be based on objectively collected data, which are assessments for the efficacy variable (HbA1c, FPG) by central laboratory blinded to study treatment groups.

As Toujeo and the control drug Tresiba are distinguishable in terms of initial dose and following doses during the first weeks of the study, a process will be applied to blind this information at the sponsor study team level.

The sponsor study team, except individuals who have access to patients' source documents (eg, local monitoring team, auditors) will remain blinded to the treatment arm of individual patients and dose of IMP throughout the study up to the database lock. All analyses and data review before database lock will be performed blindly, except for the titration review which will be performed by an independent reviewer.

Insulin titration review will be performed by reviewing the data related to fasting SMPG, hypoglycemia events and IMP dose titration by independent reviewer.

The first Statistical Analysis Plan (SAP) will be written before the first patient is randomized in the study.

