#### 8.5 METHOD OF ASSIGNING PATIENTS TO TREATMENT GROUP

The Trial Supply Operations Manager provides the treatment kit number list and the Study Biostatistician provides the randomization scheme to the interactive voice response system (IVRS)/interactive web response system (IWRS). Then, the IVRS/IWRS generates the patient randomization list according to which it allocates treatment arms to the patients.

The study medications are provided in open-label boxes and each type of kit is identified with a treatment number.

At the screening visit the investigator or designee contacts the IVRS/IWRS center to receive the patient number. The patient number is composed of 9-digit number containing the 3-digit country code, the 3-digit center code and the 3-digit patient chronological number (which is 001 for the first patient screened in a center, 002 for the second patient screened in the same center etc).

Patients are randomized to receive during the 24 weeks comparative efficacy and safety period, either Toujeo or Tresiba. The randomization ratio is 1:1. The randomization is stratified by screening HbA1c value (<8%,  $\geq8\%$ ) and SU or meglitinides use before the day of screening (Yes; No).

The treatment kits are allocated using a centralized treatment allocation system (IVRS/IWRS). On V2 (D1), after assessment results are reviewed and baseline assessment is completed, IVRS/IWRS is contacted for randomization and the first treatment kit(s) allocation. The investigator or designee has to call the IVRS/IWRS to provide some information (such as patient number provided by IVRS/IWRS at screening visit, date of birth, etc). Afterwards the IVRS/IWRS is contacted again each time a new treatment kit(s) allocation is necessary, ie, at Weeks 4, 8, 12, 16 and 20. The IVRS/IWRS will allocate treatment kit(s) using their treatment number.

A randomized patient is defined as a patient who is registered and assigned with a randomized treatment arm from the IVRS/IWRS, as documented from IVRS/IWRS log file, regardless whether the treatment kit was used or not.

A patient cannot be randomized more than once to the study.

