# 8-point SMPG Profile:

The 8-point SMPG profile should be measured at the following 8 points: the 3:00 AM (+/-1 hour) at night, pre-prandial and 2 hours postprandial for breakfast, lunch, dinner and at bedtime. Two hours postprandial (breakfast, lunch and dinner) is defined as 2 hours after the start of the meal.

The patients are requested to perform 8-point SMPG profile measurement over a single 24-hour period on at least one day in the 5 days before **baseline visit (V2)**, V14 (Week 12) and V20 (Week 24, end of treatment assessment visit). Special attention should be paid that the 3:00 AM. All SMPG values measured on these days will be recorded in the patient's diary and entered in the e-CRF (see Section 9.2.1.2.1 and Section 1.2).

On the days when 8-point profile are done, 4-point (prebreakfast, prelunch, predinner and bedtime) will be used for 4-point SMPG profile analysis.

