#### **IVRS/IWRS contact**

After the baseline assessments are completed and eligibility confirmed, the investigator contacts IVRS/IWRS for randomization. The treatment group (ie, the Toujeo or Tresiba) is notified by IVRS/IWRS.

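### Unblinded site staff and the patient may choose, with no stated criterion, which of several SMPG readings at a time point is recorded; a fixed rule is needed for the secondary SMPG endpoints (minor)

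*Protocol*

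**What the plan says.** **The choice.** Protocol 9.2.1.2.1 covers what happens at each on-site visit when the meter is downloaded. The trigger is "If the patient has more than one SMPG reading at the same time point"; in that case "the Investigator/site staff should discuss with the patient to identify the appropriate value to be recorded in the patient diary and in the e-CRF". Nothing says whether the first, the last, the mean or some other reading is to be preferred.

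**Who makes it, and when.** Protocol 8.4 states that "this study is an open-label design, and no attempt will be made to blind administration". At the baseline visit (10.1.2.1), "The treatment group (ie, the Toujeo or Tresiba) is notified by IVRS/IWRS". Under Protocol 8.5 this comes last: "after assessment results are reviewed and baseline assessment is completed, IVRS/IWRS is contacted for randomization". By the planned order, then, baseline readings are settled before the arm is known and later readings after it.

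**What is said about compensating for open label.** The paragraph under Protocol 8.4 states that "assessment of outcomes will be based on objectively collected data" and goes on to name them: "assessments for the efficacy variable (HbA1c, FPG) by central laboratory blinded to study treatment groups". SMPG is not named. The blinding described there covers the sponsor's study team, not sites or patients.

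**What else is said about recording.** For 8-point profile days, Protocol 9.2.1.2.2 says "All SMPG values measured on these days will be recorded in the patient's diary and entered in the e-CRF". The 4-point text matches it, and the fasting text asks for every available value from the week before a visit. Protocol 9.2.1.2.1 also has the meter memory printed, signed and filed, and requires e-CRF values to come from the meter output.

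**What the SAP says.** SAP 2.5.2 sets minimum counts only: 3 fasting values in 7 days, 5 of 8 profile points, 3 of 4 profile points. It has no rule for duplicates.

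**The concern.** An open-label trial can tolerate subjective steps only where they cannot reach the data being compared. Here two people who know the arm agree on one of several genuine readings, and nothing fixed in advance constrains them.

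Two distortions are possible. If the preference differs between arms, the treatment comparison of fasting SMPG or 24-hour mean glucose is shifted. If both arms simply drop the reading that looks odd, variability is understated. That matters because Protocol 9.5 includes variability in order to see whether longer, flatter insulin action steadies glucose. A measure of spread is the one most sensitive to losing extremes.

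SAP 2.4.4.2.1 compares fasting SMPG, 24-hour mean and both variability measures between arms by MMRM, so the choice feeds reported estimates and intervals.

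There is also a plain instruction problem. A site reading 9.2.1.2.1 enters one value; a site reading 9.2.1.2.2 literally enters all of them. If all are entered, the SAP does not say which is analysed.

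**Working it through.** The plan states no figure on this point, so there is none to reproduce. The check has a textual part and an illustration of size.

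**1. Does any other text remove the discretion?**

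- *Filed printout and meter-based e-CRF values (9.2.1.2.1).* These rule out invented values and make a choice auditable. They do not decide between two genuine readings, since both agree with the meter. The duty to document a reason applies to inconsistency with the meter, which does not arise.
- *Enter-all wording (9.2.1.2.2).* This may mean all scheduled points or every reading taken. On the first meaning the choice stands. On the second nothing is discarded on profile days, but the SAP then lacks a rule for which reading to use.
- *SAP 2.5.2.* Minimum counts only.

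The discretion therefore remains.

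**2. Which outcomes can it reach?**

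| Outcome | Source | Reached? |
|---|---|---|
| HbA1c (primary), FPG | Blinded central laboratory | No |
| Fasting SMPG, 24-hour mean, variability | Time-point SMPG values; MMRM | Yes, after baseline |
| 4- and 8-point profiles by time point | Time-point SMPG values; descriptive only (SAP 1.5) | Yes, after baseline |
| Hypoglycemia | Dedicated e-CRF page (Protocol 10.6.1) | Separate route |

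**3. Size: trimming of extremes.** Every input is an assumption from outside the documents.

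- True value T is normal with mean 95 or 100 mg/dL and SD 18 or 22.
- First reading a = T + e₁ and re-test b = T + e₂, with meter SD 6 or 8.
- If a ≤ 70 or a ≥ 140, a re-test is taken with probability p and the reading nearer 90 is kept. Otherwise a is kept.
- The SD of recorded values is compared with the SD of a, which equals √(SD² + meter SD²): √(18² + 6²) = 18.97 at the low end and √(22² + 8²) = 23.41 at the high end. SD stands in for variability.

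Simulating 2,000,000 readings for each of the eight combinations gives:

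| Share of extreme readings re-tested (p) | Share of all readings re-tested | Fall in recorded SD |
|---|---|---|
| All | 7 to 17% | 4.2 to 7.7% |
| One in ten | 0.7 to 1.7% | 0.4 to 0.75% |

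The smallest falls come from mean 100, SD 18, meter SD 6; the largest from mean 95, SD 22, meter SD 8. At one in ten, the mean moves by at most 0.08 mg/dL. One rule is applied to one population here, so this says nothing about a difference between arms.

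**4. Size: arm-dependent selection.** Suppose two exchangeable readings, each with SD s, and the lower is always chosen. The expected shift per duplicated time point is s/√π.

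- For s = 10, 15, 20 mg/dL: 5.6, 8.5, 11.3 mg/dL.
- If a share f of time points is duplicated and only one arm selects, the arm mean shifts by f·s/√π: from 0.02 × 5.64 = 0.1 to 0.20 × 11.28 = 2.3 mg/dL.
- If the arms select in opposite directions the difference doubles, to 0.2 to 4.5 mg/dL.

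These are worst-case behaviours. With s equal to the meter SD of step 3 (6 to 8), the one-arm shift at f = 0.20 is 0.20 × 3.39 = 0.7 to 0.20 × 4.51 = 0.9 mg/dL.

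**The case against.** The strongest reply is that this is a data-cleaning instruction with an audit trail. The meter memory is downloaded, signed and filed, so any choice is confined to genuine readings and can be checked. Fasting SMPG is asked for once a day, so duplicates are not routine. Nothing in the documents says how often patients re-test, that they do so after extreme values, or that staff prefer values near target. No between-arm bias is shown. The endpoints are secondary, and SAP 2.4.4.4 labels their p-values descriptive. All of this stands, and it sets the severity. It does not supply a criterion, which is what is missing.

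Three stronger readings are tempting and are not supported.

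- *That low readings drop out of the hypoglycemia counts.* In the simulation with every extreme re-tested, 24 to 44% of time-point values at or below 70 mg/dL are replaced. A reader might infer that the events vanish too. Protocol 10.6.1 defines asymptomatic hypoglycemia by a measured value at or below 70 mg/dL, with no exception for a reading not chosen as the time-point value, and sends all episodes to a dedicated page. The choice in 9.2.1.2.1 does not remove an event.
- *That the protocol contradicts its own claim of objective data.* The sentence in 8.4 limits that claim to HbA1c and FPG, so SMPG falls outside it.
- *That the non-inferiority result is exposed.* HbA1c comes from a central laboratory blinded to arm, so no one at the site can select it.

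The conflict with the enter-all wording is also softer than it looks, because that wording can mean all scheduled points. It is an ambiguity to reconcile rather than a proven contradiction.

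**Conclusion.** The point holds as a minor one. The protocol gives unblinded site staff and the patient an open choice between duplicate SMPG readings, its other recording instructions can be read differently, and the SAP does not settle which reading is analysed. Selection is permitted; the documents do not show that it happens.

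The exposure is limited to post-baseline fasting SMPG, the profiles, 24-hour mean glucose and, above all, variability. On the assumptions above, the fall in recorded SD runs from under 1% to about 8%, depending almost entirely on how often extreme readings are re-tested, a frequency the documents do not give. Effects on means are small unless duplicates are common and the arms behave differently. Nothing here changes how the primary analysis, FPG or hypoglycemia counts should be read.

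**What to change.** Replace the discretion in Protocol 9.2.1.2.1 with a fixed rule that does not depend on arm or on the value read:

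- The analysis value is the first valid time-stamped meter reading in the time-point window.
- A reading is set aside only for a prespecified, documented reason unrelated to its value: a meter error code, a control-solution test (sites run these on the same meters), or a reading not taken at that time point.
- All repeats are entered in the e-CRF, flagged as repeats.

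Reconcile this with the enter-all wording in 9.2.1.2.2 by saying whether it means every reading or every scheduled point. Note that a reading not used as the time-point value still falls under the hypoglycemia definitions and recording in 10.6.1. Mirror the rule in SAP 2.5.2, beside the minimum counts.

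The cost is a short protocol edit, a line in the SAP, an e-CRF completion note and slightly more data entry. The downside is that an occasional faulty first strip is kept, which adds some noise but leaves no room for a choice made with knowledge of the arm.

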#### 9.2.1.2.2 SMPG measurement

SMPG measurements include the following:

Fasting SMPG

Fasting SMPG will be used by the investigator and patients if appropriate to titrate and adjust insulin dose and to monitor glycemic control (Section 8.2.4). The fasting SMPG should be measured by the patient before breakfast and before the administration of the glucose-lowering agents once a day during the study. When up-titration has been completed and fasting SMPG is stable in the target range, at least 3 days measurements per week should be performed.

Fasting SMPG values should be recorded in the patient diary. The following daily fasting SMPG values will be entered in the e-CRF:

• All available fasting SMPG values from the week prior to each site or phone call visit and/or prior to insulin dose titration; these include the fasting SMPG value on the day of titration.

# 4-point (prebreakfast, prelunch, predinner, bedtime) SMPG Profile:

4-point SMPG profiles should be measured at the following 4 points: prebreakfast, prelunch, predinner and bedtime.

The patients are requested to perform 4-point SMPG profile measurement over a single 24-hour period on at least one day in the 5 days before V6 (Week 4) and V10 (Week 8). All SMPG values measured on these days will be recorded in the patient's diary and entered in the e-CRF (see Section 9.2.1.2.1 and Section 1.2).

On the days when 4-point profiles are done, fasting SMPG will be considered as the first point of measurement, ie, "prebreakfast" time point.

# 8-point SMPG Profile:

The 8-point SMPG profile should be measured at the following 8 points: the 3:00 AM (+/-1 hour) at night, pre-prandial and 2 hours postprandial for breakfast, lunch, dinner and at bedtime. Two hours postprandial (breakfast, lunch and dinner) is defined as 2 hours after the start of the meal.

The patients are requested to perform 8-point SMPG profile measurement over a single 24-hour period on at least one day in the 5 days before **baseline visit (V2)**, V14 (Week 12) and V20 (Week 24, end of treatment assessment visit). Special attention should be paid that the 3:00 AM. All SMPG values measured on these days will be recorded in the patient's diary and entered in the e-CRF (see Section 9.2.1.2.1 and Section 1.2).

On the days when 8-point profile are done, 4-point (prebreakfast, prelunch, predinner and bedtime) will be used for 4-point SMPG profile analysis.

# SMPG during episodes of symptomatic hypoglycemia:

Whenever the patient feels hypoglycemic symptoms, plasma glucose should be measured by the patient (or others, if applicable), if possible. Patients should be instructed to measure plasma glucose levels prior to the administration of glucose or carbohydrate intake whenever symptomatic hypoglycemia is suspected (Section 10.6.1), unless safety considerations necessitate immediate glucose/carbohydrate rescue prior to confirmation.

The SMPG values and time of SMPG measurement, relevant countermeasures, symptom of hypoglycemia, assistance required or not, will be recorded in the patient diary and e-CRF.

# Further SMPG:

The investigator may decide to request more frequent self-monitoring of plasma glucose if he/she considers necessary for the patient.

# 9.2.1.3 Dose of IMP

The patients document daily their IMP dose and time or any missed IMP injection in the patient diary.

The following values will be entered in the e-CRF:

- For the first 12 weeks (prior to V14, Week 12) of randomized treatment period:
  - Initial IMP starting dose of IMP
  - All available data on the injection time and doses administered will be entered in the e-CRF, including missed IMP injection
- After the first 12 weeks until the end of the randomized treatment period:
  - Daily dose and time of injection from the week last 3 days prior to each site or phone visit
  - In the case of any change in doses administered, the dose and injection time should be entered in the e-CRF
  - Missed IMP injection
- In case of symptomatic hypoglycemia (if appropriate), the dose and injection time should be entered in the e-CRF
- All available data of IMP dose and injection time on the last 3 days before permanently IMP treatment discontinuation

# 9.2.1.4 SU or meglitinide dose reduction/discontinuation due to hypoglycemia

The type and dose of antidiabetic background therapy will remain unchanged during the study but may have identified safety concerns necessitating a reduction in dose or discontinuation. The changes in antidiabetic medication administration and its reason should be documented in source data. If the dose reduction/discontinuation is due to hypoglycemia, the reason should be documented in e-CRF and report hypoglycemia event, eg, SU and meglitinide dose reduction due to hypoglycemia.

# 9.2.2 Safety endpoints

The safety endpoints are assessed by:

• Hypoglycemia events

Property of the Sanofi Group - strictly confidential

Hypoglycemia will be classified as below category and analyzed using the following variables:

- Percentage of patients with at least one episode of confirmed hypoglycemia\* and event rate during 24 weeks treatment periods,
- Rate of hypoglycemia per month computed as: 365.25/12 x (number of episodes of hypoglycemia)/(number of days exposed in time window),
- Percentage of patients and event rate of hypoglycemia by study period (for ≤12 weeks, for >12 weeks to ≤24 weeks) to evaluate the potentially increased risk of hypoglycemia during the initial 12-week after starting treatment with basal insulin,
- The diurnal distribution of the occurrence of each episode of confirmed hypoglycemia by category will be presented by two-hour timeframe over 24 hours during the 24 weeks treatment period.
- \* Note: Confirmed hypoglycemia: Any hypoglycemia confirmed by plasma glucose below the cut off value (70 or 54 mg/dL). The cut-off value of 70 mg/dL (3.9 mmol/L) for defining hypoglycemia is in line with ADA hypoglycemia definition. The cut-off value of 54 mg/dL (3 mmol/L) is chosen because it represented a degree of hypoglycemia at which patients have typically neuroglycopenic symptom.
- Adverse events (AE) or serious adverse events (SAE), including local tolerability at injection site, hypersensitivity reactions, Adverse events with special interest (AESI),
- Vital signs,
- Body weight.

